10.0 Data and Safety Monitoring Plan

Given the minimal risk nature of this observational study, monitoring will be conducted by the CISTO Executive Committee. The CISTO Executive Committee consists of the chair, the co-PIs, the director of the Data Coordinating Center (DCC), the director of the Clinical Coordinating Center (CCC), and stakeholder representatives covering expertise in clinical epidemiology, biostatistics, and urologic oncology. The CISTO Executive Committee meets monthly and time during one Executive Committee

meeting per quarter will be set aside to review any data and safety events and procedures and to determine recommendations for these events and procedures as appropriate. This briefing will cover the following procedures:

- Monitoring study safety
- Minimizing research-associated risk
- Protecting the confidentiality of participant data
- Identifying, reviewing, and reporting adverse events (AEs) and serious adverse events (SAEs) and unanticipated problems to the applicable IRB(s) or other monitoring bodies
- Procedures for ensuring compliance with the DSMP and the requirements for reporting across research study sites.

10.1 SAE Reporting

Participants will be monitored for SAEs throughout their study surveillance period (enrollment through up to four-year follow-up). The occurrence of an SAE may come to the attention of study personnel during study follow-up phone interview, by UW study staff personnel conducting follow-up, or by a study participant calling the study team or presenting for medical care. If an SAE comes to the attention of study personnel via patient, caregiver, or family report, the site research coordinator will be notified that an SAE form needs to be completed. The site research coordinator will then use the EMR to fill out the SAE form. The site PI will then complete the form and sign the form. The SAE form will then be submitted to the DCC who will provide it to the CISTO Executive Committee. The CISTO Executive Committee will review the SAE form and ask the site PI for additional clarification or specification as they see necessary.

SAEs are defined as one of the following conditions:

1. Death during the period of protocol-defined surveillance;
2. Life-threatening event related to the treatment or significant disability/incapacity related to the treatment;
3. Inpatient hospitalization (other than for cystectomy);
4. Prolonged hospitalization following cystectomy (14 days or more).

All SAEs will be:

1. Recorded on the SAE case report form;
2. Followed until satisfactory resolution or until the study investigators deem the event to be chronic or the participant to be stable;
3. Reported to the study investigators, the project managers, and site IRBs per their reporting guidelines.

CISTO is an observational study using procedures or treatments with well-established risk profiles. There is no reason to suspect the risk profiles in the proposed study population would differ. The number of adverse events and related unexpected serious adverse events (SAEs) will be summarized descriptively by arm, by grade and body system. The proportion of participants experiencing each toxicity will be summarized by maximum National Cancer Institute's Common Terminology Criteria for Adverse Events (NCI CTCAE) grade²¹ experienced, overall and by arm.

The local and systemic side effects associated with intravesical therapy will be graded according to the International Bladder Cancer Group's (IBCG) recommendations²² (percentage indicates incidence rate):

- Cystitis noninfective (33-80%)

- Hematuria (up to 90%)
- Urinary tract obstruction (rare)
- Urinary tract infection
- Prostate infection (1-3%)
- Epididymoorchitis (0.2-10%)
- Rash maculo-papular (up to 19%)
- Malaise (30.5%)
- Fever (5-20%)
- Allergic reactions (rare)
- Myelosuppression (rare – anemia/neutropenia/thrombocytopenia)
- Pelvic pain
- Renal colic

The systemic side effects associated with immunotherapy (pembrolizumab) will be graded and reported as per previous reports²³⁻²⁵ (percentage indicates incidence rate):

- Fatigue (11-29%)
- Pruritus (10-22.7%)
- Hypothyroidism (7-21.1%)
- Hyperthyroidism (5-11.9%)
- Arthralgia (4-22.1%)
- Pneumonitis (3-4.1%)
- Dry mouth (3%)
- Asthenia (2-10.2%)
- Aspartate aminotransferase increased (2%)
- Myalgia (2%)
- Cough
- Headache
- Increase in blood creatinine level

Operative radical cystectomy is a major operation that has a number of recognized complications and a low risk of death (less than 2 in 100). Expected adverse events will be graded using the Clavien Dindo classification²⁶ and reported as per previous reports^{27,28} (percentage indicates incidence rate):

- Gastrointestinal (29%): ileus, small intestinal obstruction, constipation, enterocolitis infectious, upper gastrointestinal hemorrhage, lower gastrointestinal hemorrhage, vomiting, small intestinal anastomotic leak, diarrhea, colonic obstruction, dehydration, and nausea.

- Infectious (25%): abdominal infection, urinary tract infection, sepsis, gastritis and cholecystitis.
- Wound (15%): seroma, wound infection and wound dehiscence.
- Genitourinary (11%): acute kidney injury, urinary tract obstruction, ureteric anastomotic leak, urethral anastomotic leak, urinary fistula, urinary retention, parastomal hernia, gastrointestinal stoma necrosis and hematuria.
- Cardiac (11%): ventricular arrhythmia, myocardial infarction, hypertension, heart failure, chest pain-cardiac and hypotension.
- Pulmonary (9%): atelectasis, lung infection, dyspnea, pneumothorax and pleural effusion.
- Bleeding (9%): anemia and postoperative hemorrhage.
- Thromboembolic (8%): thromboembolic event and phlebitis.
- Neurological (5%): peripheral motor neuropathy, transient ischemic attacks, delirium, vertigo, depressed level of consciousness and seizure.

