## 8. Data and Safety Monitoring Plan (DSMP)

The CISTO Study adheres to a Data Safety Monitoring Plan. Given the minimal risk nature of this observational cohort study, monitoring is conducted by the study's Executive Committee. On a monthly basis, the Executive Committee reviews any data and safety events and procedures and determine recommendations for these events and procedures as appropriate, including identifying, reviewing, and reporting adverse events (AEs) and serious adverse events (SAEs) and unanticipated problems to the applicable Institutional Review Boards (IRBs) or other monitoring bodies. SAEs are defined as 1) death during the study period; 2) life-threatening event related to the treatment or significant disability/incapacity related to the treatment; 3) inpatient hospitalization (other than for cystectomy); and 4) prolonged hospitalization following cystectomy (14 days or more). The number of adverse events and related unexpected serious adverse events (SAEs) will be summarized by arm, by recruitment site, by grade, and by the National Cancer Institute's Common Terminology Criteria for Adverse Events (CTCAE) system organ class. In addition, for each toxicity, the proportion of affected participants overall and by arm will be summarized by the maximum CTCAE grade experienced. The interim review of SAEs will not lead to recommendations towards study recruitment or discontinuation.

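### The SAE definition exempts the cystectomy stay from the hospitalisation criterion, so SAE counts by arm are not like for like and tend to miss serious, non-life-threatening complications of that stay

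*Protocol*

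**What the plan says.** Protocol 10.1 defines an SAE by four alternative criteria:

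1. Any death while the patient is under study surveillance.
2. A threat to life, or serious disability, that is attributed to treatment.
3. Admission to hospital, worded as "Inpatient hospitalization (other than for cystectomy").
4. A long surgical stay, worded as "Prolonged hospitalization following cystectomy (14 days or more").

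SAP 8 gives the same four without change. Criterion 3 carries no minimum stay and no relatedness condition. Criterion 4 is the only route by which the length of a cystectomy stay makes it an SAE.

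On reporting, Protocol 10.1 says: "The number of adverse events and related unexpected serious adverse events (SAEs) will be summarized descriptively by arm, by grade and body system". SAP 8 plans the same kind of summary by arm and adds recruitment site. It also says that "for each toxicity, the proportion of affected participants overall and by arm will be summarized by the maximum CTCAE grade experienced". Protocol 10.1 plans Clavien-Dindo grading for cystectomy complications and describes the listed ones as expected.

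Two statements in Protocol 9.1 decide how the rule falls across the arms. Arms are defined by the treatment chosen at enrollment. All or almost all of the cystectomy arm is expected to have surgery before the 12-month endpoint, against up to 20% of the medical-management arm.

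**The concern.** The threshold for calling an event serious depends on whether it happens during a cystectomy stay. Urinary tract infection, hematuria and urinary tract obstruction appear in Protocol 10.1 both among the side effects of intravesical therapy and among the complications of cystectomy. A patient admitted overnight for one of these meets criterion 3. A patient who develops the same problem during the cystectomy stay, without threat to life or lasting disability, and who goes home before day 14, meets none of the four criteria. The same holds for listed surgical events such as wound dehiscence, anastomotic leak or acute kidney injury when they stay below criteria 1 and 2.

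The study exists to inform a choice between surgery and bladder-sparing treatment. A reader who compares SAE counts by arm will assume that one standard was applied throughout. Neither document warns that part of any difference could come from the definition.

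**Working it through.** The documents give no SAE rate, no length-of-stay distribution and no SAE-based power, so there is no planned figure to reproduce. The check has two parts: reading the criteria side by side, and an illustrative count.

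**Part 1: which events count**

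| Event | Is it an SAE? | Criterion |
|---|---|---|
| Death, either arm, any setting | Yes | 1 |
| Treatment-related life-threatening event or disability, including during a cystectomy stay of any length | Yes | 2 |
| Any admission not for cystectomy, either arm, any length or cause | Yes | 3 |
| Readmission after cystectomy | Yes | 3 |
| Cystectomy stay of 14 days or more, either arm | Yes | 4 |
| Other serious complication within a cystectomy stay under 14 days, either arm | No | none |

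Only the last row falls through. It applies to a procedure, so its effect on the arm comparison depends on how many patients in each arm have that procedure.

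**Part 2: how much this could shift the counts**

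Inputs from the documents:
- Arm sizes: 235 cystectomy and 337 medical management (Protocol 9.4).
- Share of the medical arm having cystectomy within 12 months: c, from 0 up to 20% (Protocol 9.1). At 20%, 0.20 × 337 = 67.4 patients.
- Share of the cystectomy arm having surgery: taken as all, from the same section.

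Input assumed, because the documents do not give it:
- q: the share of cystectomies with a last-row complication, at one per patient. Range shown: 5% to 20%.

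Formulas:
- Uncounted in the cystectomy arm = 235 × q.
- Uncounted in the medical arm = 337 × c × q.
- Difference in uncounted events per 100 patients = 100 × q × (1 − c).

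Results at c = 20%:

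| q | Cystectomy arm (of 235) | Medical arm (of 337) | Difference, percentage points |
|---|---|---|---|
| 5% | 235 × 0.05 = 11.8 | 67.4 × 0.05 = 3.4 | 5 × 0.8 = 4 |
| 10% | 235 × 0.10 = 23.5 | 67.4 × 0.10 = 6.7 | 10 × 0.8 = 8 |
| 20% | 235 × 0.20 = 47.0 | 67.4 × 0.20 = 13.5 | 20 × 0.8 = 16 |

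At c = 0 the medical-arm column is zero and the differences are 5, 10 and 20 points. For any q above zero and any c below 1, the direction is the same: more uncounted events per patient in the cystectomy arm. SAE surveillance runs for up to four years, and any later cystectomies in the medical arm would raise c and narrow the gap.

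**The case against.** Four arguments on the other side carry weight.

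*The exemption is sensible.* Without it, almost every cystectomy patient would be an SAE case because of a planned operation. This stands. The gap concerns complications inside the stay, not the decision to exempt the stay.

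*The by-arm SAE summary may not show the effect.* Both documents describe the SAEs to be summarised as related and unexpected, and Protocol 10.1 calls the listed cystectomy complications expected. Applied strictly, that filter would remove those complications even if they were SAEs, and it would also remove unrelated medical-arm admissions. This also stands: the definition's own effect on that table is then smaller, and the net tilt in it cannot be stated. But lifting the filter would not restore the missing events, because they were never labelled SAEs.

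*The information is reported elsewhere.* Adverse events are summarised by arm and grade whatever their SAE status, cystectomy complications receive Clavien-Dindo grades, and 12-month hospital days are a secondary outcome with no stated exclusion of the cystectomy stay. This limits the harm. It does not make the SAE counts comparable.

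*SAE counts are not an outcome of the study.* Neither document lists them among the primary or secondary outcomes, and SAP 8 says that interim SAE review will not lead to recommendations on recruitment or discontinuation. This stands and keeps the point small.

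Three stronger readings are tempting but unsupported. A reader might infer that the rule favours one arm by name; it does not, since it follows the procedure in both arms and counts readmissions. A reader might infer that a cystectomy stay counts only from day 14; criteria 1 and 2 apply at any length. A reader might also take the listed incidences of gastrointestinal (29%) and infectious (25%) complications, about 68 and 59 of 235 patients, as a base for counting missed SAEs. Those lists include nausea, constipation and urinary tract infection. The documents give no serious fraction and no split between the index stay and later, so the percentages cannot yield a count of missed serious events.

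**Conclusion.** The asymmetry is real and is the same in both documents. One class of event goes uncounted: a serious complication of the cystectomy stay that is not fatal and not a treatment-related life-threatening or disabling event, with a stay under 14 days. Because the two arms differ so much in how many patients have a cystectomy, SAE counts by arm tend to run low in the cystectomy arm.

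The direction follows from the text; the size does not. The illustrative range of about 12-47 uncounted events against about 3-13, or 4-16 percentage points, rests on an assumed 5-20% complication share, one such event per patient, surgery in all of the cystectomy arm, and 20% later cystectomy in the medical arm. It also describes SAE counts before any restriction to related and unexpected events.

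The documents do not support saying that the study as a whole hides surgical harm, because the graded adverse-event summaries remain. This is a minor to moderate point about a descriptive safety summary and does not touch any outcome analysis.

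**What to change.** Leave the SAE definition unchanged for reporting to the Executive Committee and the IRBs. In the by-arm safety summary (Protocol 10.1 and SAP 8), add three separate rows:

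- complications of the cystectomy stay graded Clavien-Dindo III or higher, whatever the length of stay;
- hospitalisations other than the cystectomy stay;
- deaths.

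Do not add the rows into one total. Clavien-Dindo grading is planned only for surgery, so a pooled count would still mix two thresholds. Do not restrict these rows to related and unexpected events, or the index-stay complications could drop out again as expected. Add a footnote that the cystectomy stay is exempt from the hospitalisation criterion in both arms, and state whether the main SAE table covers all SAEs or only the related and unexpected ones.

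The cost is a change to the table specification. Protocol 6.6 already provides for abstracting cystectomy and adverse-event data, and the grading is already planned. The downside is a slightly larger table and a higher visible count of serious events in the cystectomy arm.

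### The by-arm SAE summary is limited to related, unexpected events, so the plan has no by-arm count of all the SAEs it defines and records

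*Protocol*

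**What the plan says.** Protocol 10.1 defines four kinds of SAE. Three carry no condition on cause or expectedness: "Death during the period of protocol-defined surveillance"; "Inpatient hospitalization (other than for cystectomy"); and "Prolonged hospitalization following cystectomy (14 days or more"). Only the remaining kind, a life-threatening or disabling event, must be related to treatment. Each SAE goes on a form that is sent to the Data Coordinating Center and passed to the Executive Committee.

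The tabulation rule in the same section is narrower: "The number of adverse events and related unexpected serious adverse events (SAEs) will be summarized descriptively by arm, by grade and body system". SAP 8 keeps the restriction: "The number of adverse events and related unexpected serious adverse events (SAEs) will be summarized by arm, by recruitment site, by grade". It adds CTCAE system organ class. Neither document plans another by-arm table of SAEs.

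Later in Protocol 10.1 the list of cystectomy complications is introduced with "Expected adverse events will be graded using the Clavien Dindo classification". It has nine groups with incidence rates, beginning "Gastrointestinal (29%): ileus, small intestinal obstruction, constipation, enterocolitis infectious, upper gastrointestinal hemorrhage". The lists for intravesical therapy and pembrolizumab are headed as side effects and do not carry the word expected.

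Both documents also plan, for each toxicity, the share of participants at each maximum CTCAE grade, overall and by arm, with no filter on expectedness.

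**The concern.** The study collects SAEs under a broad definition and then summarises them by arm under a narrow one. Filtering on related and unexpected suits alerts to a review board, where the question is whether something new has happened. It suits a description of two established treatments less well, because most of what can go seriously wrong with such treatments is already known. Protocol 10.1 itself says that both have well-established risk profiles.

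Aim 1 compares patient-centered clinical outcomes, and Hypothesis 2.1 supposes that patients avoid cystectomy out of concern about its complications. How many deaths, readmissions and prolonged stays followed each choice is a question such readers will ask. The safety table as specified would not answer it.

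**Working it through.** No figure in the plan needs reproducing. The check sets the definition beside the tabulation rule and then asks what the documents allow one to say about size.

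**1. Definition against rule.** I take related to mean related to treatment, and unexpected to mean not on the protocol's expected list.

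| SAE type (Protocol 10.1) | Condition in the definition | Left out of the by-arm SAE summary when |
|---|---|---|
| Death | none | unrelated, or judged expected |
| Life-threatening or disabling event | related to treatment | due to a listed complication |
| Inpatient admission, except for cystectomy | none | unrelated, or due to a listed complication |
| Post-cystectomy stay of 14 days or more | none | unrelated, or due to a listed complication |

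The last type exists only because of the operation, yet it would be counted only when its cause is both related and off the list. Death is not itself an item on the list. The protocol mentions only an operative risk below 2 in 100, that is, fewer than 0.02 × 235 = 4.7 deaths in the cystectomy arm. Whether such a death is expected is left open.

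**2. Breadth of the list.** The nine rates sum to 29 + 25 + 15 + 11 + 11 + 9 + 9 + 8 + 5 = 122%. With the 235 cystectomy patients of Protocol 9.4, that is 1.22 × 235 = 286.7 patient-category events. Patients with at least one listed event number at least 0.29 × 235 = 68. If the categories were independent (an assumption), the share would be 1 − (0.71 × 0.75 × 0.85 × 0.89 × 0.89 × 0.91 × 0.91 × 0.92 × 0.95) = 0.74, or 174 patients. These are rates at any severity and include nausea and constipation. They show that the list is broad, not how many events are serious.

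**3. Share of SAEs kept.** Let e be the share of cystectomy SAEs due to listed events, and q the share of the remainder that is related. The share kept is (1 − e) × q. The documents give neither quantity. For assumed values of e from 0.50 to 0.95 and q from 0.5 to 1.0, the share kept runs from 0.05 × 0.5 = 2.5% to 0.50 × 1.0 = 50%. This shows only how strongly the result depends on unknown inputs.

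**4. Both arms are affected.** Protocol 9.1 defines arms by the choice at enrollment and allows that up to 20% of medical management patients may have a cystectomy within 12 months: 0.20 × 337 = 67. Surgical SAEs will therefore occur, and be filtered, in both arms. The cystectomy arm is more exposed, since nearly all of its 235 patients are expected to have the operation.

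**5. What other outcomes supply.** By-arm adverse event counts and the maximum-grade table keep the events but not their status as a death, readmission or prolonged stay. Hospital days give total use, with no stated split between the index stay and later admissions, or by cause. The secondary outcomes in both documents include several cancer-related survival measures but do not list overall survival. SAP 4.4 uses death only to set quality-of-life scores to the floor in a sensitivity analysis. None of these gives a by-arm count of SAEs as defined.

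**The case against.** The strongest reply is that little is lost. The sentence with the filter also counts all adverse events by arm, and the maximum-grade table follows. Hospital days and cancer-related survival are secondary outcomes. The rule sits in the safety monitoring section of a minimal-risk observational study, the protocol calls the summary descriptive, and SAP 8 says that interim SAE review will not bear on recruitment or discontinuation. Unexpected is undefined, so an investigator could call a listed event unexpected because of its severity. Recording and review of individual SAEs are unaffected. All of this stands and limits the point. It does not supply the missing count.

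Three stronger readings are tempting, and the documents support none of them.

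- A reader might infer that most serious surgical harm disappears from the comparison of arms. The events remain in the by-arm adverse event tables, and whether most SAEs leave the SAE summary depends on shares that the documents do not give.
- A reader might apply a guessed serious fraction to the listed rates to obtain a number of uncounted SAEs. Those rates cover any severity and overlap within patients, and many complications during the index stay meet none of the four SAE types.
- A reader might infer that grades cannot be compared across arms, because cystectomy events use Clavien Dindo and intravesical side effects "will be graded according to the International Bladder Cancer Group's (IBCG) recommendations". Both documents already prescribe maximum CTCAE grade for the by-arm toxicity table, and the other systems can be read as treatment-specific additions. A conflict of scales is not established.

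**Conclusion.** The point holds as a gap in reporting. As written, both documents leave out of the by-arm SAE summary every unrelated SAE in either arm and, on the natural reading of unexpected, SAEs caused by recognised cystectomy complications. The plan therefore has no by-arm count of deaths, readmissions and prolonged stays as SAEs, although it collects each of them. The size cannot be stated from the documents.

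For unrelated SAEs the conclusion rests on the wording alone, with related read as related to treatment. For surgical complications it also rests on linking unexpected to the protocol's own list, which is an inference. Information on harm as such is not lost.

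**What to change.** In Protocol 10.1 and SAP 8, replace *related unexpected* SAEs in the by-arm summary with all serious adverse events as defined in Protocol 10.1. Show them by the four SAE types, and keep related and unexpected SAEs as a subset. State what unexpected is judged against, since that subset still depends on it.

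The cost is one wording change in each document and a wider table. No new data collection is needed, because the SAE forms already reach the Data Coordinating Center. The SAE counts will look less favourable than under the present rule, so a note should say that they include expected and unrelated events.

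### Protocol 10.1 grades cystectomy complications by Clavien-Dindo, yet the planned by-arm toxicity summary is on maximum CTCAE grade, and neither document says where that grade comes from

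*Protocol*

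**What the plan says.** Two sets of rules appear in the same protocol section.

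**How events are summarized.** Protocol 10.1 has adverse events and related unexpected serious events "summarized descriptively by arm, by grade and body system". Each toxicity is then "summarized by maximum National Cancer Institute's Common Terminology Criteria for Adverse Events (NCI CTCAE) grade", overall and by arm. SAP section 8 agrees: for each toxicity, "the proportion of affected participants overall and by arm will be summarized by the maximum CTCAE grade experienced". It also groups events by CTCAE system organ class and by recruitment site.

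**How events are graded.** Protocol 10.1 gives three instructions, one per treatment:
- Radical cystectomy: "Expected adverse events will be graded using the Clavien Dindo classification".
- Intravesical therapy: "The local and systemic side effects associated with intravesical therapy will be graded according to the International Bladder Cancer" Group's recommendations.
- Pembrolizumab: systemic effects "will be graded and reported as per previous reports", with no scale named.

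SAP section 8 mentions neither Clavien-Dindo nor IBCG. Protocol 9.1 defines the arms by the patient's choice at enrollment and expects up to 20% of those who choose medical management to have a cystectomy within 12 months.

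**The concern.** The grading instructions and the summary rule do not meet. A site that grades a cystectomy complication exactly as Protocol 10.1 instructs produces a Clavien-Dindo grade. The analyst who follows SAP section 8 needs a CTCAE grade. No sentence in either document supplies the second from the first, requires both, or sends the Clavien-Dindo grades to a table of their own.

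The clarity of the harms display is at stake. Protocol 2.1 frames the treatment decision as progression risk against the morbidity of bladder removal, and the by-arm toxicity summary is where that morbidity is shown by grade. If surgical grades are absent, the cystectomy column understates graded toxicity. If Clavien-Dindo grades are entered as though they were CTCAE grades, part of any visible difference between columns reflects the scale. A maximum grade per participant also has no clear meaning for someone whose events were graded on two scales.

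**Working it through.** The documents give no figure to reproduce here. The check sets the rules side by side and then counts who could be affected.

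**Step 1. Grading rule against summary rule.**

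| Treatment received | Grading source (Protocol 10.1) | Scale of the by-arm summary (Protocol 10.1, SAP 8) | Link stated? |
|---|---|---|---|
| Radical cystectomy | Clavien-Dindo (reference 26) | Maximum CTCAE grade (reference 21) | None |
| Intravesical therapy | IBCG recommendations (reference 22) | Maximum CTCAE grade | None |
| Pembrolizumab | Previous reports (references 23 to 25), scale not named | Maximum CTCAE grade | None |

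Clavien-Dindo and CTCAE are named and referenced as separate instruments, the former as a classification of surgical complications. The first row is therefore a documented mismatch. In the second and third rows the grading sources are not reproduced, so their distance from CTCAE cannot be judged.

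**Step 2. Terms on both lists.** Matching the intravesical and cystectomy lists in Protocol 10.1 gives four shared terms: hematuria, urinary tract infection, urinary tract obstruction, and anemia (under myelosuppression on one list and bleeding on the other). As written, each is graded by IBCG after intravesical therapy and by Clavien-Dindo after cystectomy, but falls under one toxicity heading in the by-arm summary.

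**Step 3. Mixing within an arm.** Inputs: 337 medical-management patients (Protocol 9.4) and crossover of up to 20% (Protocol 9.1). 0.20 × 337 = 67.4, so at most about 67 patients in that arm could have a cystectomy within 12 months. Any surgical complications among them would be graded by Clavien-Dindo while being counted under medical management. The reverse can also occur: SAP 4.3 foresees patients whose first treatment belongs to the other arm.

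**Step 4. How many cystectomy-arm patients could have events on the surgical scale.** Inputs: 235 patients anticipated (Protocol 9.4) and the category incidences listed in Protocol 10.1. Assume that all 235 have surgery and that the listed rates apply to them.
- Lower bound, from the largest single category (gastrointestinal, 29%): 0.29 × 235 = 68.2, about 68 patients.
- Upper bound, from adding all categories: 29 + 25 + 15 + 11 + 11 + 9 + 9 + 8 + 5 = 122%. This exceeds 100%, so the sum sets no limit below 235. Categories can overlap within a patient.

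The listed figures therefore support a range from about 68 to 235 and do not locate the number within it.

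**The case against.** The strongest reply is that both documents name one scale for the toxicity table, CTCAE, and that SAP section 8 also groups events by CTCAE system organ class. On that reading every event is CTCAE-coded for the by-arm table, and the treatment-specific tools are additional. Nothing in Protocol 10.1 says that a Clavien-Dindo grade replaces a CTCAE grade, and the adverse-event form is not among the documents, so a CTCAE field may already exist. This stands as a possibility. It does not close the gap, because dual grading is never instructed and the only explicit grading instructions point to other sources.

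A second reply is that the summary is descriptive, with no test planned, and that toxicity grade is in neither the primary nor the secondary outcome list (Protocol 7.1 and 7.2, SAP 2 and 3). This is correct and limits the consequence. A descriptive table set out by arm still needs one scale, since readers will compare its columns.

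Some stronger readings are tempting but unsupported:
- A reader might infer that each arm has its own scale. The source follows the treatment received, and the medical-management arm alone can carry all three.
- A reader might infer that IBCG and pembrolizumab grades are incompatible with CTCAE. Those sources cannot be checked from the documents, and either could use CTCAE.
- A reader might infer that essentially all 235 cystectomy patients would have events on the surgical scale. That treats having the operation as having a complication.

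**Conclusion.** The point holds as a conflict between stated rules. Protocol 10.1 prescribes Clavien-Dindo for cystectomy events, while Protocol 10.1 and SAP section 8 summarize by arm on maximum CTCAE grade, with no stated route from one to the other. The table can be filled consistently only if every event is also CTCAE-graded, which neither document requires. It does not follow that the table will mix scales. That outcome depends on what sites actually record.

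The effect is confined to descriptive safety reporting. The QLQ-C30 physical functioning endpoint, its analysis and the power statement are untouched. Within safety reporting the affected events are not rare by the protocol's own incidences. The crossover figure of about 67 is a ceiling on operations, not a count of patients with graded complications. The conclusion rests on the absence of any linking instruction in the two documents. An adverse-event form or abstraction manual that already requires a CTCAE grade for every event would reduce this to a wording correction.

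**What to change.** Reconcile Protocol 10.1 with SAP section 8:

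1. In Protocol 10.1 and on the adverse-event form, require a CTCAE term and grade for every adverse event, regardless of treatment received.
2. In SAP section 8, state that this grade alone feeds the by-grade, by-arm and maximum-grade tables.
3. Report Clavien-Dindo and IBCG grades in separate tables as descriptions within treatment, neither pooled nor compared across arms.
4. For events already abstracted with only a Clavien-Dindo grade, assign a CTCAE grade from the abstracted record where it allows. Show the remainder in a separate table with no between-arm comparison of grade.

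The cost is one form field if none exists, a sentence or two in each document, and some back-coding. The first analytic data set was due to be frozen on March 14, 2024, the date of the SAP itself, so the back-coding would fall after that freeze and before the final refresh estimated for January 2025 (SAP 1.6). Protocol 6.6 already includes adverse events in record abstraction, which should help. Where the abstracted record is too thin to grade, sites would have to go back to the chart or the event would go to the separate table, so the workload depends on how many events carry only a Clavien-Dindo grade.
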